5.6 Removal of Subjects from Study

Subjects can be taken off the study treatment and/or study at any time at their own request, or they may be withdrawn at the discretion of the investigator for safety, behavioral or administrative reasons. The reason(s) for discontinuation will be documented and may include:

- 5.5.1 Subject voluntarily withdraws from treatment (follow-up permitted);
- 5.5.2 Subject withdraws consent (termination of treatment and follow-up);
- 5.5.3 Subject is unable to comply with protocol requirements;
- 5.5.4 Subject experiences toxicity that makes continuation in the protocol unsafe;
- 5.5.5 Treating physician judges continuation on the study would not be in the subject's best interest;
- 5.5.6 Subject becomes pregnant (pregnancy to be reported along same timelines as a serious adverse event); or
- 5.5.7 Lost to follow-up. If a research subject cannot be located after a period of 2 months, the subject may be considered "lost to follow-up." All attempts to contact the subject during the 2 months must be documented.

6.0 RESPONSE CRITERIA

6.1 Safety/tolerability

Analyses will be performed for all subjects having received at least one dose of study drug. CBC, CMP, EKG will be performed on all subjects to monitor for toxicities and safety.

6.2 Efficacy

Increase in quantity of food that can be ingested on oral food challenge, decreased skin prick tests and decreased basophil activation will be used to assess efficacy of the treatment.

7.0 ADVERSE EVENTS

7.1 Experimental Therapy

For the most recent safety update, please refer to the current Study Agent Prescribing Information. (This drug is currently FDA approved for alternate indications. Sections below are from the current package insert).

7.1.1 Contraindications

None.

7.1.2 Special Warnings and Precautions for Use

Prior studies of ibrutinib adverse events were performed on cancer patients who had often failed other treatments, and were treated chronically. However, Advani et. al. (13) reported side effects in a phase 1 study for only 28 days, the shortest duration of treatment that has been reported in the literature. In that study, a total of 56 patients with a variety of relapsed B-cell malignancies were treated over seven dosage cohorts (1.25 - 12 mg/kg/day). For the cohort receiving dosages closest to the one being used in our study (a total of 6 subjects given 5 mg/kg/day, or 420 mg/day for an 81 kg person) the most common adverse events were typically grade 1 or 2 in severity. Grade 3 or 4 events were infrequent and independent of dose. Data from this cohort of 6 subjects was extracted and reproduced from Table 3 of the Advani et. al. paper below. For the entire cohort of 56 subjects, Grade 3-4 hematologic toxicities included neutropenia (12.5%), thrombocytopenia (7.2%) and anemia (7.1%). According to the authors, no evidence of cumulative hematologic or non-hematologic toxicity was observed in patients with prolonged dosing, nor was any consistent relationship seen between dose level and adverse events.

	Diarrhea	Nausea/vomiting	Constipation	Decreased appetite/dyspepsia	Fatigue	Insomnia	Headache	Muscle spasms/myalgia	Other pain	Pyrexia	Rash	Cough	Other respiratory	Arthralgia	Edema
Grade 1-2	1	3	2	1	0	1	1	2	5	2	0	3	3	2	1
Grade 3-4	1	0	0	0	0	0	0	0	0	0	0	0	1	0	0

As the subjects enrolled in this study will be generally healthy except for food allergy, and on ibrutinib for a much shorter duration (maximum of 7 days, perhaps as little as 2 days), we expected adverse events to be milder and less frequent, if at all, compared to prior studies of ibrutinib in cancer trials. However, for completeness, adverse events as documented with chronic use are detailed below.

7.1.2.1 Hemorrhage

Five percent of patients with MCL had Grade 3 or higher bleeding events (subdural hematoma, gastrointestinal bleeding, and hematuria). Overall, bleeding events including bruising of any grade occurred in 48% of patients with MCL treated with 560 mg daily.

The mechanism for the bleeding events is not well understood.

7.1.2.2 Infections

Fatal and non-fatal infections have occurred with ibrutinib therapy. At least 25% of patients with MCL had infections Grade 3 or greater NCI Common Terminology Criteria for Adverse Events CTCAE) (14).

7.1.2.3 Myelosuppression

Treatment-emergent Grade 3 or 4 cytopenias were reported in 41% of patients. These included neutropenia (29%), thrombocytopenia (17%) and anemia (9%). Monitor complete blood counts monthly.

7.1.2.4 Renal Toxicity

Fatal and serious cases of renal failure have occurred with ibrutinib therapy. Treatment- emergent increases in creatinine levels up to 1.5 times the upper limit of normal occurred in 67% of patients and from 1.5 to 3 times the upper limit of normal in 9% of patients. Periodically monitor creatinine levels. Maintain hydration.

7.1.2.5 Embryo-Fetal Toxicity

Based on findings in animals, ibrutinib can cause fetal harm when administered to a pregnant woman. Ibrutinib caused malformations in rats at exposures 14 times those reported in patients with MCL receiving the ibrutinib dose of 560 mg per day. Reduced fetal weights were observed at lower exposures. Advise women to avoid becoming pregnant while taking ibrutinib. If this drug is used during pregnancy or if the patient becomes pregnant while taking this drug, the patient should be apprised of the potential hazard to a fetus.

7.1.3 Interaction with other medications

As stated, metabolism of ibrutinib is inhibited by CYP3A inhibitors. Patients on these medications will be excluded.

7.1.4 Adverse Reactions

As per package insert (15), adverse reactions are listed in Section 7.1.2. Of note, patients in the trial references took a larger dose and for much longer duration than we propose in this study.

The most commonly occurring adverse reactions (approx. 20%) were thrombocytopenia, diarrhea, neutropenia, anemia, fatigue, musculoskeletal pain, peripheral edema, upper respiratory tract infection, nausea, bruising, dyspnea, constipation, rash, abdominal pain, vomiting and decreased appetite.

The most common Grade 3 or 4 non-hematological adverse reactions (approx. 5%) were pneumonia, abdominal pain, atrial fibrillation, diarrhea, fatigue, and skin infections.

Adverse reactions from the MCL trial (N=111) using single agent IMBRUVICA 560 mg daily occurring at a rate of approx. 10%.

Ten patients (9%) discontinued treatment due to adverse reactions in the trial (N=111). The most frequent adverse reaction leading to treatment discontinuation was subdural hematoma (1.8%). Adverse reactions leading to dose reduction occurred in 14% of patients.

Patients with MCL who develop lymphocytosis greater than 400,000/mcL have developed intracranial hemorrhage, lethargy, gait instability, and headache. However, some of these cases were in the setting of disease progression.

Forty percent of patients had elevated uric acid levels on study including 13% with values above 10 mg/dL. Adverse reaction of hyperuricemia was reported for 15% of patients.

8.0 ADVERSE EVENT MONITORING

Adverse event data collection and reporting, which are required as part of every clinical trial, are done to ensure the safety of Subjects enrolled in the studies as well as those who will enroll in future studies using similar agents. Adverse events are reported in a routine manner at scheduled times during a trial. Additionally, certain adverse events must be reported in an expedited manner to allow for optimal monitoring of subject safety and care.

All subjects experiencing an adverse event, regardless of its relationship to study drug/device, will be monitored until:

- the adverse event resolves or the symptoms or signs that constitute the adverse event

- return to baseline;
- any abnormal laboratory values have returned to baseline;
- there is a satisfactory explanation other than the study drug for the changes observed; or
- death.

8.1 Definitions

8.1.1 Definition of Adverse Event

An adverse event (AE) is any untoward medical occurrence in a subject receiving study treatment and which does not necessarily have a causal relationship with this treatment. An AE can therefore be any unfavorable and unintended sign (including an abnormal laboratory finding), symptom, or disease temporally associated with the use of an experimental intervention, whether or not related to the intervention.

8.1.2 Severity of Adverse Events

The severity of an AE is graded as follows:

Mild (grade 1): the event causes discomfort without disruption of normal daily activities.

Moderate (grade 2): the event causes discomfort that affects normal daily activities.

Severe (grade 3): the event makes the subject unable to perform normal daily activities or significantly affects his/her clinical status.

Life-threatening (grade 4): the subject was at risk of death at the time of the event.

Fatal (grade 5): the event caused death.

8.1.3 Serious Adverse Events

A “serious” adverse event is defined in regulatory terminology as any untoward medical occurrence that:

8.1.3.1 Results in death.

If death results from (progression of) the disease, the disease should be reported as event (SAE) itself.

8.1.3.2 Is life-threatening.

(the subject was at risk of death at the time of the event; it does not refer to an event that hypothetically might have caused death if it were more severe).

-
- 8.1.3.3 Requires in-subject hospitalization or prolongation of existing hospitalization for ≥ 24 hours.
 - 8.1.3.4 Results in persistent or significant disability or incapacity.
 - 8.1.3.5 Is a congenital anomaly/birth defect.
 - 8.1.3.6 Is an important medical event.

Any event that does not meet the above criteria, but that in the judgment of the investigator jeopardizes the subject, may be considered for reporting as a serious adverse event. The event may require medical or surgical intervention to prevent one of the outcomes listed in the definition of "Serious Adverse Event". For example: allergic bronchospasm requiring intensive treatment in an emergency room or at home; convulsions that may not result in hospitalization; development of drug abuse or drug dependency.

8.2 Steps to Determine If an Adverse Event Requires Expedited Reporting

Step 1: Identify the type of adverse event.

Step 2: Grade the adverse event.

Step 3: Determine whether the adverse event is related to the protocol therapy
Attribution categories are as follows:

- Definite – The AE *is clearly related* to the study treatment.
- Probable – The AE *is likely related* to the study treatment.
- Possible – The AE *may be related* to the study treatment.
- Unrelated – The AE *is clearly NOT related* to the study treatment.

Note: This includes all events that occur within 30 days of the last dose of protocol treatment. Any event that occurs more than 30 days after the last dose of treatment and is attributed (possibly, probably, or definitely) to the agent(s) must also be reported accordingly.

Step 4: Determine the prior experience of the adverse event.

Expected events are those that have been previously identified as resulting from administration of the agent. An adverse event is considered unexpected, for expedited reporting purposes only, when either the type of event or the severity of the event is not listed in:

- the current known adverse events listed in the Agent Information Section of this protocol;
- the drug package insert;
- the current Investigator's Brochure

8.3 Reporting Requirements for Adverse Events

8.3.1 Expedited Reporting

- The Principal Investigator must be notified within 24 hours of learning of any serious adverse events, regardless of attribution, occurring during the study or within 30 days of the last administration of the study drug.
- The Northwestern University IRB must be notified within 5 business days of any unanticipated problems involving risk to subjects or others (UPIRSO).

The following events meet the definition of UPIRSO:

1. Any serious event (injuries, side effects, deaths or other problems), which in the opinion of the Principal Investigator was unanticipated, involved risk to subjects or others, and was possibly related to the research procedures.
2. Any serious accidental or unintentional change to the IRB-approved protocol that alters the level of risk.
3. Any deviation from the protocol taken without prior IRB review to eliminate apparent immediate hazard to a research subject.
4. Any new information (e.g., publication, safety monitoring report, updated sponsor safety report), interim result or other finding that indicates an unexpected change to the risk/benefit ratio for the research.
5. Any breach in confidentiality that may involve risk to the subject or others.
6. Any complaint of a subject that indicates an unanticipated risk or that cannot be resolved by the Principal Investigator.
7. The FDA should be notified within 7 business days of any unexpected fatal or life-threatening adverse event with possible relationship to study drug, and 15 business days of any event that is considered: 1) serious, 2) unexpected, and 3) at least possibly related to study participation.

8.3.2 Routine Reporting

All other adverse events- such as those that are expected, or are unlikely or definitely not related to the study participation- are to be reported annually as part of regular data submission.

8.3.3 Stopping Rules

The study will be stopped if >50% of patients cannot complete the protocol due to toxicities or adverse events.

9.0 DRUG INFORMATION

9.1 Ibrutinib 140 mg tablets

- Other names for the drug(s)/device: Imbruvica®
- Classification - type of agent/device: small molecule BTK inhibitor

Mode of action: Ibrutinib forms a covalent bond with a cysteine residue in the BTK active site, leading to inhibition of BTK enzymatic activity. BTK is a signaling molecule of the B-cell antigen receptor (BCR) and cytokine receptor pathways. BTK's role in signaling through the B-cell surface receptors results in activation of pathways necessary for B-cell trafficking, chemotaxis, and adhesion. Nonclinical studies show that ibrutinib inhibits malignant B-cell proliferation and survival in vivo as well as cell migration and substrate adhesion in vitro.

- Storage and stability: Ibrutinib is stored at room temperature and the tablets are stable.
- Protocol dose: 420 or 560 mg once daily for 2-7 days
- Preparation: as supplied from the manufacturer
- Route of administration for this study: By mouth
- Incompatibilities: N/A

- Availability: commercially available by prescription. Medication will be paid for through NIH funding, and provided free of charge to subjects.
- Side effects: Most common side effects are diarrhea, nausea, fatigue and musculoskeletal pain. Other side effects include myelosuppression, bleeding and hepatotoxicity. Please refer to package insert for comprehensive list of side effects.
- Nursing implications: Ibrutinib is category D. It should not be used in nursing mothers.

9.2 Return and Retention of Study Drug

Study drug will be obtained by the research pharmacy at Northwestern Feinberg School of Medicine by prescription only. Study drug will be dispensed as needed, until next follow up. Therefore, we do not anticipate retention of study drug. However, if there is unused study drug, it will be disposed of in an appropriate manner.

9.2.1 Compliance will be assessed by subject diary and self-report.

10.0 STATISTICAL CONSIDERATIONS

Descriptive statistics will be completed to determine an 80% reduction in skin prick wheal size and basophil activation test reactivity (as determined by % inhibition of anti-IgE-induced CD63 expression). As this is an open label study, each patient's responsiveness will be examined compared to themselves prior to initiation of treatment.

10.1 Study Design/Study Endpoints

This is an open label study of ibrutinib in 12 food allergic adults to determine the shortest amount of time and fewest ibrutinib doses required to eliminate food SPT and BAT reactivity and to evaluate the effect of pretreatment with ibrutinib on food allergen reactivity in food allergic subjects given ibrutinib 420 or 560 mg daily for 2-7 doses. Given the nature of the study, it will be stopped if >50% of patients have a DLT at target enrollment.

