1.2 Study Drug Background and Associated Known Toxicities

Ibrutinib is a once daily, oral, selective, irreversible small-molecule inhibitor of Bruton's tyrosine kinase (BTK), a key component of B-cell receptor signaling (8,9). BTK is also essential for Fc ϵ RI signaling and triggering of mast cells and basophils (10){Iyer, 2011 #10272;Kuehn, 2008 #10273;MacGlashan, 2011 #8797}. It is currently FDA approved for the treatment of Mantle Cell Lymphoma (MCL), Chronic Lymphocytic Leukemia (CLL) and Waldenstrom's macroglobulinemia (WM).

In subjects with recurrent B-cell lymphoma, >90% irreversible occupancy of the BTK active site in peripheral blood mononuclear cells was observed up to 24 hours after ibrutinib doses of \geq 2.5 mg/kg/day. Ibrutinib is absorbed with a median Tmax of 1-2 hours. It is metabolized by cytochrome P450 and CYP3A, and has a half-life of 4-6 hours. The majority (80%) is fecally excreted.

The approved CLL and WM dose (420 mg orally once daily) has been shown to inhibit allergy test responses in cancer subjects receiving this drug by 1 week of treatment (the earliest time point examined) in preliminary data from our group. The 560 mg dose (used for MCL) has similar side-effect and toxicity profiles as the lower dose. Initial data from Part 1 suggests that the 420mg dose can at least partially (in some cases fully) inhibit skin test responses to peanut and tree nuts in allergic subjects after just 2 doses, with minimal side effects and no observed toxicity thus far in subjects taking ibrutinib for up to 7 days. Therefore, we can justify using the higher dose of 560 mg orally once daily for Part 2 to investigate whether this higher dose can further reduce skin test responses beyond what is seen with the lower dose.

In human studies, ibrutinib is metabolized in the liver, and not significantly renally cleared. In healthy volunteers, co-administration with CYP3A inhibitors increased Cmax, and therefore the drug will not be concomitantly administered with strong or moderate inhibitors of CYP3A. Known toxicities in cancer subjects receiving ibrutinib chronically include bleeding events (5% of MCL subjects), infection (25% of MCL subjects), myelosuppression (41% of subjects), and renal toxicity has also been reported. Ibrutinib is also pregnancy category D. This underscores our goal of finding the fewest possible doses to achieve the anti-allergy effect we are seeking, which could be as few as just 2 doses.

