3.3 Study Stopping Criteria

The study will be stopped if >50% of patients cannot complete the protocol due to toxicities or adverse events. Toxicities (section 4.2) and adverse events (section 7.0) are listed below. Monitoring is described in section 8.0.

[figure not shown]

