4.0 TREATMENT PLAN

4.1 Treatment Dosage and Administration

For Part 1 of the study, we will determine the length of treatment (i.e., the number of daily doses) required to inhibit both basophil and food skin test responses. Preliminary data demonstrates that 7 days of treatment will inhibit both basophil and mast cell responsiveness to aeroallergens, but have not yet tested shorter time points. Prior studies in cancer subjects suggest that one dose is sufficient to completely inhibit BAT, but we propose a minimum of two doses to allow for diffusion and penetration of ibrutinib into the skin compartment where our SPT is performed to assess skin mast cell responsiveness. For Part 1, 6 subjects will take ibrutinib 420 mg, by mouth once daily (every 24 hours) on an outpatient basis. After two days, the subject will undergo blood testing and SPT to assess basophil and mast cell reactivity. If both tests are negative, Part 1 is completed. If both tests are not negative, then the subject will take 2 more days of ibrutinib (same dose, for a total of 4 doses), and identical testing will be repeated. If testing is not negative at day 4, the subject will take 3 more days of ibrutinib (same dose, for a total of 7 doses), which is the maximum anticipated number of doses needed to suppress both the BAT and SPT.

For Part 2 of the study, 6 subjects will take ibrutinib 560 mg once daily by mouth (every 24 hours) for 2 days, which is the minimum number of days required to cause $\geq 80\%$ inhibition of food SPT and BAT responses as determined in part 1. Part 2 will last a minimum of 3 days.

Dose-limiting toxicity (DLT) includes any grade 3 or 4 hematologic toxicity, grade 3 hepatotoxicity or increase in creatinine $\times 2.5$ normal limit. DLT will be monitored at each visit, at any time during treatment.

Maximally tolerated dose (MTD) will occur at the point DLT occurs. Ibrutinib is approved as a daily medication for another indication, and we propose to use the drug in adults only at its approved oral dosing of 420 or 560 mg daily for a minimum of two days and a maximum of 7 days. Dose limiting events include grade 3 or 4 hematologic events, grade 3 or 4 hepatotoxicity, AST or ALT >3 times normal range, creatinine >2.5 times normal range. DLT evaluation will be completed throughout the study, anytime during treatment.

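### Read naturally, the >50% stopping rule pools both dose parts, so after an event-free Part 1 it cannot be met in Part 2

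*Combined protocol and SAP*

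**What the plan says.** The study-level stopping rule appears three times in the combined protocol and SAP.

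- Section 10.1: "Given the nature of the study, it will be stopped if >50% of patients have a DLT at target enrollment".
- Section 3.3: "The study will be stopped if >50% of patients cannot complete the protocol due to toxicities or adverse events". Section 8.3.3 repeats this sentence.

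The first counts dose-limiting toxicities (DLTs) and fixes a time point. The other two count non-completion and fix none. None names a part or a dose.

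The denominator comes from two places. Section 10.1 opens: "This is an open label study of ibrutinib in 12 food allergic adults". Section 4.1 splits them: "For Part 1, 6 subjects will take ibrutinib 420 mg, by mouth once daily", and "For Part 2 of the study, 6 subjects will take ibrutinib 560 mg once daily by mouth".

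Section 1.2 supports the move to the higher dose partly with the experience in Part 1, "with minimal side effects and no observed toxicity thus far in subjects taking ibrutinib for up to 7 days".

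**The concern.** A stopping rule should be able to stop the study in the situation where it is most needed. Here that is Part 2, which combines the higher dose with a provoked allergic reaction at the food challenge, under a primary objective (2.1.1) of changing challenge thresholds safely. If both parts share one denominator, a clean Part 1 dilutes whatever happens in Part 2. The same clean result that supports the higher dose then puts the stopping threshold out of reach.

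Timing adds to this in section 10.1. A rule read when the enrolment target has been reached can no longer limit enrolment.

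**Working it through.** **Inputs.** Six subjects in each part (4.1); 12 in total (10.1); threshold strictly greater than 50% (3.3, 8.3.3, 10.1); no Part 1 toxicity so far (1.2). Section 4.6 replaces voluntary withdrawals who tolerated the drug, which can only hold or raise the denominator. It does not replace toxicity dropouts, who count as DLTs.

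**The plan's own figure.** 6 + 6 = 12, as stated.

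**Events needed when pooled.** The smallest k with k/12 > 0.5 is 7, because 6/12 = 0.500 does not qualify.

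**Part 1 event-free, denominator 12.** The maximum is (0 + 6)/12 = 50.0%. The rule is not met, so the probability of stopping is 0 at every true Part 2 rate, including 100%.

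**Part 1 event-free, subjects dosed to date as denominator.** In the worst case every Part 2 subject has an event, and the fraction after k subjects is k/(6 + k): 14.3%, 25.0%, 33.3%, 40.0%, 45.5% and 50.0% for k = 1 to 6. It never exceeds 50%. The cap also applies to the rule in 3.3 and 8.3.3, even if every Part 2 toxicity counts as non-completion.

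**One Part 1 event.** With denominator 12, (1 + 6)/12 = 58.3% meets the rule but (1 + 5)/12 = 50.0% does not, so all six Part 2 subjects must have an event. On a running denominator, 6/11 = 54.5% would meet it once the first five Part 2 subjects had all had an event.

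**Sensitivity to the Part 1 rate.** Suppose all six Part 2 subjects have a DLT. The pooled rule at 12 is then met only if Part 1 had at least one, with probability 1 − (1 − p₁)⁶. For assumed Part 1 rates p₁ of 5% and 10% this is 0.265 and 0.469.

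**The same threshold within Part 2.** More than 50% of 6 means at least 4. With X binomial:

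- By the sixth subject, P(X ≥ 4 | n = 6). At 50%: (15 + 6 + 1)/64 = 0.344. At 80%: 0.2458 + 0.3932 + 0.2621 = 0.901.
- By the fifth subject, P(X ≥ 4 | n = 5). At 50%: (5 + 1)/32 = 0.188. At 80%: 0.4096 + 0.3277 = 0.737.

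| True Part 2 rate | Pooled rule after 0/6 in Part 1 | Part 2 alone, by fifth subject | Part 2 alone, by sixth subject |
|---|---|---|---|
| 50% | 0 | 0.19 | 0.34 |
| 80% | 0 | 0.74 | 0.90 |
| 100% | 0 | 1.00 | 1.00 |

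The fifth-subject column is the protective one, since a sixth subject can still be spared. It assumes that each result is known before the next subject is dosed; the documents do not say whether Part 2 dosing is staggered.

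**The case against.** The best reply is that pooling is inferred. No section says in words that the parts share a denominator, and section 4.1 plans six subjects in each. That stands: pooling is the natural reading of a rule about patients in a study of 12, not an explicit statement. The ambiguity itself needs resolving.

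A second reply is that pooling is defensible, because 1.2 describes similar toxicity profiles at the two doses and 7.1.2 reports no consistent relation with dose. Those statements rest on cancer patients, and a safety rule should not depend on the assumption that it is there to check.

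Four stronger readings are tempting, and the documents do not support them.

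- *Nothing else protects subjects.* Section 4.2 stops drug for the individual, 4.1 monitors DLTs at each visit, and 8.3.1 requires notice of serious events to the investigator within 24 hours and of unexpected risk/benefit changes to the IRB. Expected events "are to be reported annually as part of regular data submission" under 8.3.2, but that governs outward reporting, not what a single-centre investigator sees. What is missing is another numeric study-level criterion: the maximum tolerated dose sentence in 4.1 names no study action, and section 8.0, to which 3.3 points for monitoring, sets no running count beyond repeating the rule.
- *At target enrolment nobody is left to protect.* The Study Schema puts at least two weeks between the Part 2 baseline challenge and dosing, so some enrolled subjects may still be undosed. The timing phrase is also in 10.1 only.
- *Sections 3.3 and 8.3.3 cannot register a Part 2 toxicity because both doses are already taken.* They refer to completing the protocol, which includes the on-drug challenge and the follow-up at 3 and/or 6 months. What limits them is the 6/12 cap.
- *The rule can never stop the trial.* One Part 1 event makes 7/12 reachable, and 1.2 reports only on Part 1 to date.

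**Conclusion.** The point holds. After an event-free Part 1 of six subjects, the probability of meeting the pooled rule in Part 2 is exactly 0, whatever the true rate on 560 mg. Within Part 2 alone, the same threshold would be met with the probabilities in the table.

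The conclusion rests on four things: the pooled reading, the strict inequality, the planned six and six, and no Part 1 events with Part 1 complete before Part 2 events accrue. Had only five event-free Part 1 subjects been dosed, 6/11 = 54.5% would exceed the threshold on an untimed reading. Section 4.1 makes Part 1 first the expected order, since it takes the two-day Part 2 schedule from Part 1 results.

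This is a defect in how the study-level rule is written. It does not show that subjects are without other safeguards, and it affects no efficacy estimate.

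**What to change.** Reconcile sections 3.3, 8.3.3 and 10.1 into one rule:

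1. State one event definition, DLT or inability to complete the protocol. The choice is the sponsor's.
2. Keep the sponsor's >50% threshold, but apply it to the six planned subjects of each part, so that it is met at the fourth event in a part.
3. Replace the reading at target enrolment in 10.1 with a running review after each subject.
4. Name the role that keeps the count, and describe the review in section 8.0.

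If the sponsor does intend to pool, the text should say so and acknowledge that Part 2 cannot meet the rule after an event-free Part 1.

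The cost is wording in these sections and a tally for 12 subjects at one centre. The downside is that a part could stop earlier. At true rates of 20% and 30%, the chance of at least 4 of 6 is 0.0154 + 0.0015 + 0.0001 = 0.017 and 0.0595 + 0.0102 + 0.0007 = 0.070.
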